5.2 Method for Assigning Subjects to Treatment Groups

All 20 patients with epilepsy and depression will be enrolled into the treatment group. All patients will have dense array EEG and MRI.

5.3 Subject Compliance Monitoring

Because a research RN or a trained TMS study team member will deliver the TMS treatments, treatment compliance will be monitored throughout administration. The RN or study team member will ensure that the subject does not fall asleep during the treatment sessions.

5.4 Prior and Concomitant Therapy

Subjects past antiseizure medications will be obtained from the medical history. Subjects antidepressant medication/treatment history will be obtained at screening using the Antidepressant Treatment History Form. Subjects may remain on a stable dose of their antidepressant and anti-seizure medications during the study. No antiepileptic or anti-depressant medication changes during the study will be allowed unless medically necessary.

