3.2 Primary Study Endpoints

1. Change in weekly seizure rate as assessed by self-report seizure log.
2. Change in significant side effects as assessed by the Systematic Assessment for Treatment Emergent Events (SAFTEE)[50].
3. Feasibility of participation such that 80% of patients will complete the study protocol including all measures, MRI, dense array EEG, and TMS.
4. Correlation of pre and post TMS hemispheric frontal alpha power asymmetry, anterior cingulate theta power, and frontotemporal alpha coherence with changes in depression severity.

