4.1 Inclusion Criteria

Participants will be recruited from the epilepsy patient population within the Department of Neurology at Dartmouth-Hitchcock Medical Center. Screening and baseline evaluations will be performed by a board-certified neurologist and psychiatrist as well as a research coordinator trained to reliably administer structured interviews and rating scales. 20 participants will be recruited with the following initial inclusion criteria:

- Females or males age 18 and older.
- Able and willing to provide informed consent.
- Diagnosis of probable epilepsy (focal or generalized) confirmed by the study neurologist.
- English-speaking
- Not pregnant
- Able to safely undergo MRI (as assessed by MRI safety form).
- Have a family member or friend (proxy) who will be able to bring the patient to the hospital and serve as a safety monitor for two consecutive nights.
- Patients on stable doses of current antiepileptic and antidepressant medications for 1 month.

Once patients fulfill initial inclusion criteria, they will be referred to see the study psychiatrist who along with a research coordinator will determine if patient meets the following further inclusion criteria:

- Diagnosis of a depressive episode of any severity (including, mild, moderate, and severe) by the study psychiatrist (Quick Inventory of Depression Severity-Subject Rated [QIDS] score >6 or Neurologic Disorders Depression Inventory – (NDDI-E) score of > 15).
- Inadequate response to at least one antidepressant medication during the current episode.

Exclusion Criteria

Patients will be excluded if the following criteria are met:

- Significant cognitive impairment (Montreal Cognitive Assessment [MOCA] <23)
- History of other major psychiatric disorders (e.g., schizophrenia, bipolar disorder,) or presence of unstable medical comorbidities, which the investigators agree, will interfere with adherence and/or safety.
- Active substance use disorder that the investigators agree will interfere with adherence and/or safety.
- Actively/imminently suicidal (QIDS item 12 score > 2 or MINI Suicidality module score > 16)
- Greater than 10 seizures per week during 1 month prior to treatment, confirmed by the study neurologist.
- History of stroke, moderate-severe traumatic brain injury or other major neurological disorder, which the study neurologist feels will interfere with adherence and/or safety.

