6.9 Visit 8: 3-month follow up

- 3 months after visit 5 (+/- 4 weeks), the patient will be contacted by a research staff member over the phone.
- Research staff will administer the QIDS and SAFTEE in addition to checking the patient's seizure log.

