6.10 Visit 9: 6-month follow up

- 6 months after Visit 5 (+/- 4 weeks) the patient will return to DHMC for a follow up with the study neurologist, coordinator, and psychiatrist.
- Research staff will administer the MoCA, QIDS, and SAFTEE. Seizure log will be reviewed.
- Neuropsychological testing (QOLIE-31, MAC-S, RBANS) will be done by research staff.
- Medication review will be done with patient or through review of electronic medical record.
- A dense-array EEG test will be conducted, which may include EEG tasks.

7 Statistical Plan

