7.1 Statistical Methods

The study will be closely monitored for safety parameters with stopping rules as defined in Section 8.7. At the conclusion of the study, baseline demographics and clinical characteristics will be summarized with means, proportions and associated standard deviations. For safety, occurrence rates of SAE (seizures or hospitalizations) will be estimated and exact binomial confidence intervals will be formed. Very few if any are expected in this small study. The SAFTEE scale will be compared before and after TMS with independent t-tests based on the individual changes from baseline. The study completion rates will be estimated and compared to the target rate of 80% using exact tests for binomial data.

The secondary outcomes will be measured before and after treatment using dense-array EEG biomarkers and depression scores along with test results during functional MRI and EEG. Paired t-tests will be used to compare *change* in depression severity, memory, executive functioning, quality of life, and social cognition from baseline to endpoint. MRI patterns of activation will be analyzed. Analysis of variance for repeated measures will be used to test task and neuropsychological testing results.

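### Data collected after a permitted antiepileptic or antidepressant change enter the QIDS and seizure-rate changes unmarked, and can dilute or reverse a worsening there

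*Combined protocol and SAP*

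**What the plan says.** Drug therapy is meant to be steady. Section 4.1 requires "Patients on stable doses of current antiepileptic and antidepressant medications for 1 month", and Section 5.4 then says: "No antiepileptic or anti-depressant medication changes during the study will be allowed unless medically necessary". The exception has no end date short of the end of the study, and Section 6.10 sets the last visit: "6 months after Visit 5 (+/- 4 weeks) the patient will return to DHMC".

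The outcomes that a drug change would touch are these:

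- Section 3.2, endpoint 1: "Change in weekly seizure rate as assessed by self-report seizure log". No time window is given.
- Section 7.1, safety: "occurrence rates of SAE (seizures or hospitalizations) will be estimated and exact binomial confidence intervals will be formed". This is the only seizure analysis described. No method is given for the change in weekly rate.
- Section 7.1, secondary outcomes: paired t-tests of change in "depression severity, memory, executive functioning, quality of life, and social cognition from baseline to endpoint". The endpoint visit is not named.
- Section 7.3: safety is analysed in patients who start, and secondary outcomes in those who complete TMS. Neither set depends on later medication.

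Sections 7.1 to 7.3 do not mention medication changes at all. After TMS, Sections 6.8 and 6.10 list a medication review at Visits 7 and 9. At Visit 8, Section 6.9 says that "the patient will be contacted by a research staff member over the phone", and lists QIDS, SAFTEE and the seizure log. Visit 6 (Section 6.7) is also a call with those three items.

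**The concern.** The plan controls medication before entry and restricts it afterwards, so drug changes are evidently regarded as something that could disturb the outcomes. The analysis nevertheless treats a QIDS score or a log week obtained under a new drug like any other. It is plausible, though the documents do not show it, that changes made for medical need fall largely on patients who have worsened. If the new drug works, the later data look better, and the before-and-after change attributes this to TMS.

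All patients receive TMS and nobody is blinded (Sections 5.2 and 5.5), so no comparison group can reveal the effect. Endpoint 1, the depression comparison and Hypothesis 2a, which correlates EEG changes with depression changes, would all inherit it. The direction would be toward a smaller apparent harm on seizures and a larger apparent benefit on depression.

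**Working it through.** **1. What is collected, and when (Sections 6.6 to 6.10)**

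| Contact | QIDS | Seizure log | Medication review listed |
|---|---|---|---|
| Visit 5, third TMS day | yes | yes | no |
| Visit 6, 1 week, call | yes | yes | no |
| Visit 7, 1 month | yes | yes | yes |
| Visit 8, 3 months, call | yes | yes | no |
| Visit 9, 6 months | yes | yes | yes (patient or electronic record) |

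Between the two listed reviews lie nominally 6 − 1 = 5 months. The study visit guide, procedures table and monitoring plan (Attachments B, C and E) are not in the text available for this review and may list more.

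**2. The plan's own figure**

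Section 7.2 gives a detectable change in depression of 0.764 SD for a two-sided paired t-test at 0.05 with power 0.90. With n = 20, 19 degrees of freedom and the noncentral t distribution, the detectable effect is 0.7645 SD, and power at 0.764 is 0.8997. The figure reproduces and serves as the yardstick in step 4.

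**3. Weekly seizure rate (illustration; every rate and duration is assumed)**

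Mean rate = (r1 × w1 + r2 × w2) / (w1 + w2), with six months taken as 26 weeks and a baseline of 1 per week.

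- Rate 2 for 4 weeks, then back to 1 after a drug change: (2 × 4 + 1 × 22) / 26 = 30/26 = 1.15. The doubling appears as +15%.
- Rate 2 for 8 weeks, then 1: (2 × 8 + 1 × 18) / 26 = 34/26 = 1.31, or +31%.
- Rate 2 for 4 weeks, then 0.5: (2 × 4 + 0.5 × 22) / 26 = 19/26 = 0.73. The patient appears to improve by 27%.
- Data up to the drug change only: 2.0, or +100%, in all three cases.

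The 26-week average is one possible reading of endpoint 1. The plan does not prescribe it. A window confined to the last weeks would show no change in the first two cases.

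**4. Depression score (illustration; k and s are assumed)**

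If k of 20 patients change medication and each final score moves s SD toward improvement because of the drug, the mean change moves by k × s / 20 SD. The last column is the chance that the two-sided test rejects when the mean change without the drug effect is 0, with the SD of changes held at 1.

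| k | s | Shift in mean (SD) | Share of 0.764 | Chance of rejection |
|---|---|---|---|---|
| 1 | 0.5 | 0.025 | 3% | 0.05 |
| 2 | 1 | 0.10 | 13% | 0.07 |
| 4 | 1 | 0.20 | 26% | 0.14 |
| 4 | 2 | 0.40 | 52% | 0.40 |
| 6 | 2 | 0.60 | 79% | 0.72 |

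In practice the SD would move as well, in a direction that depends on which patients are shifted. The last column is therefore rough; the shift in the mean is not affected. The documents give neither the share of patients who change medication nor the effect of a change, so the table shows a range and not an estimate.

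**5. What still records the worsening**

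- Section 8.1 makes worsening of a preexisting condition an adverse event, and keeps increases in seizure frequency and in depressive symptoms reportable after day 30.
- Section 8.1 gives a seizure without admission as an example that is usually serious, and Section 7.1 analyses SAE occurrence. Later improvement does not undo an occurrence.
- Section 8.7 counts patients with increased seizure frequency and patients with significantly worse depression.
- QIDS and the log are read at Visits 5, 6 and 7. In the 4-week example, the doubled rate would be in the log by about Visit 7.

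**The case against.** The strongest reply is that this pilot's stated safety analysis is event-based, so little depends on averages over follow-up. That stands, and it limits the point. A reader might infer that treating a TMS-related worsening erases it from the results. The documents do not support that: the provisions in step 5 keep the worsening visible, and only late change scores can lose it.

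A reader might also infer that the plan contains a seizure-rate analysis that ignores medication. It does not; Section 7.1 has no analysis of endpoint 1. The gap lies in what remains to be specified: once a method and window are written, they need a rule for drug changes too.

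Three further objections have weight. The depression effect depends on the unnamed endpoint: at Visit 5 drug changes would hardly matter, at Visit 9 they could. The direction is plausible but not shown, since drugs may also be changed for tolerability; and a patient restored to baseline shows no change rather than benefit, so reversal needs a drug effect beyond baseline. Finally, the timing of changes need not rest on recall: Visit 9 allows review of the electronic record, and Section 8.4 requires adverse event questioning at every contact. That questioning, however, targets events, and does not ensure that the date and reason of a drug change are recorded.

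Making the up-to-change analysis primary would be debatable, because it drops late data from patients selected by their course. So would adding medication increases to a count that stops the trial. Neither is proposed.

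**Conclusion.** The point holds in limited form. Changes are allowed for the whole follow-up, the statistical sections do not separate the data before from the data after them, and the listed medication reviews leave the two calls uncovered. In a single-arm design this can dilute or reverse a worsening in late QIDS changes and in any weekly seizure-rate change. Adverse event and SAE reporting and the Section 8.7 counts still capture it.

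The size is unknown. The 1.15 and 0.73 per week and the shifts of 0.025 to 0.60 SD rest on assumed rates, durations, numbers of patients and drug effects, and on a 26-week window that the plan does not set. This is a worthwhile and inexpensive improvement, not a defect that invalidates the safety assessment.

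**What to change.** In Section 7.1:

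1. Name the visit that serves as the depression endpoint, and the baseline and follow-up windows for the weekly seizure rate.
2. Report the change in QIDS and in weekly seizure rate twice: on all data, and on data up to the first relevant medication change (antidepressant for QIDS, antiepileptic for seizures, or either for both if the sponsor prefers). Present them side by side, since stopping at the change is itself informative.
3. For Hypothesis 1.a, also report the number of patients with either an increased seizure rate or an antiepileptic increase or addition made because of increased seizures.

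In Sections 6.7 and 6.9, add one item to the existing Visit 6 and Visit 8 calls: the date of, and reason for, any antiepileptic or antidepressant change.

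The Section 8.7 stopping counts and clinical care stay unchanged. The cost is a few sentences of analysis text, one question in two calls, a little more analysis work, and fewer late data points in the up-to-change results.

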5.5 Blinding of Study Device

Neither the patient nor the physician will be blinded and all patients will receive treatment.

6 Study Procedures

Recruitment and initial screening by the study Neurologist may take place at DHMC- Manchester. All other study visits will take place at Dartmouth-Hitchcock Medical Center (DHMC) in Lebanon, NH.

6.1 Visit 1a: Initial Screening by Neurologist – Pre-enrollment

- Patient will review and sign informed consent.
- Initial screening will be done by a board-certified neurologist (, Visit 1a). Patient's history and physical will be taken, medications will be reviewed, seizure log, MOCA will be performed if time permits. All incomplete assessments may be done at Visit 1b.
- Subject will receive seizure log and instructions for its use.

6.2 *Visit 1b: Initial Screening by Psychiatrist – Pre-enrollment*

- Subsequent evaluation will be done by board-certified psychiatrist and research assistant Visit 1b). If the subject is unable to complete the full screening during Visit 1a, he or she may be scheduled for a second screening appointment with study psychiatrist and research assistant. At that time, diagnosis of medication-resistant depression will be confirmed; the MINI, QIDS, SAFTEE, PANAS MRI safety, TASS and ATHF will be performed. Seizure log data will be obtained.
- If time permits, Visit 2 procedures can be done at Visit 1b.

6.3 *Visit 2: Imaging and Baseline Neuropsychological Testing – Pre Enrollment*

- Patient will be report to the Advanced Imaging Center for MRI. MRI will last approximately one hour.
- After MRI is complete, patient will be brought to the EEG lab . A dense-array EEG will be conducted which will take approximately one hour.
- Patient will do neuropsychological and social-cognition testing, which will last approximately 2 hours. (QOLIE-31, RBANS and MAC-S)
- If time permits, TMS motor threshold may be done at Visit 2, so long as TMS treatment is scheduled to begin within one week. Otherwise, TMS motor threshold will be done at Visit 3.

6.4 *Visit 3: Enrollment and first day of TMS treatment*

- Patient will be brought to DHMC by their proxy for the first day of TMS treatment.
- Research staff will administer the QIDS, SAFTEE, and PANAS. Data will be obtained from the patient's seizure log.
- Patient will be given TMS motor threshold test to calibrate the machine for treatment, if not done at Visit 2. Following calibration, the designated TMS trained study team member or study RN will begin administering the first TMS treatment session under supervision of the study psychiatrist . Each treatment session will last approximately 50 minutes, and the patient will be given the opportunity to take a break between sessions. The patient will be scheduled to receive four, and may receive as many as seven, treatment sessions by the end of Visit 3.
- Following the final TMS session, study personnel will administer the SAFTEE, and PANAS.
- Following TMS, the family member/proxy will be instructed how to monitor the patient for safety, and he or she will be given contact information in case of unusually strong seizures. A hotel room will have been booked by study personnel prior to the study visit, if needed. The proxy will stay in the same room as the patient between all treatment days.
- The study Neurologist will be on call in case of unusual seizures.
-

6.5 *Visit 4: Second day of treatment*

- The proxy will bring the patient back to DHMC, and report to the Psychiatry Clinic for Visit 4.
- Research staff will administer the SAFTEE and PANAS. Seizure log will be reviewed.
- After completing assessments, the subject will begin the planned seven treatment sessions. Break times will be provided between sessions if desired.
- At the end of the final treatment session, research staff will:
 - Administer the SAFTEE and PANAS.
 - Remind the patient and proxy about contact and safety information before they depart.
- The study Neurologist will remain on call in case of unusually strong seizures.

6.6 *Visit 5: Third day of treatment*

- The proxy will bring the patient back to the Psychiatry Clinic for Visit 5.
- Research staff will administer the SAFTEE, PANAS. Seizure log will be reviewed.
- The patient will have four planned treatment sessions, but may receive as many as seven treatment sessions, with the opportunity to rest between trains.
- Once the final TMS treatment session is complete, a second dense-array EEG test will be conducted, which will last approximately one hour.
- After completion of the dense-array EEG, research staff will:
 - Administer the SAFTEE, PANAS, QIDS, and MoCA.
 - Debrief patient and proxy. Provide with safety information.
- Patient will be taken home by proxy*.

*If the subject has not completed the 15 treatment sessions by the end of Day 3, they will be given the option to return to the TMS clinic for one more day to receive the remaining TMS treatment.

- The study Neurologist will remain on call in case of unusually strong seizures.

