1.5 Dose Rationale and Risk/Benefits

Low-frequency (LF) TMS refers to TMS delivered at a frequency of 1 Hz or below. Unlike HF TMS, LF TMS can decrease cortical excitability and may have anticonvulsant effects[42]. Low frequency TMS applied to right DLPFC also has an extensive though smaller database supporting its antidepressant efficacy, and comparisons to left HF DLPFC TMS suggest both treatments work equally as well[43, 44]. Surprisingly, LF TMS has not been investigated as an antidepressant treatment in patients with epilepsy, though it would have clear advantages compared to HF TMS including increased tolerability and potentially anticonvulsant effects.

2 Study Objectives

Specific Aim 1: To examine the safety and feasibility of accelerated low-frequency transcranial magnetic stimulation (TMS) to the right dorsolateral prefrontal cortex in patients with epilepsy and comorbid depression.

Hypothesis 1.a. (safety): Treatment will not produce serious adverse events defined as an increase in seizure rate or hospitalization.

Hypothesis 1.b. (safety): Treatment will not be associated with a higher rate of adverse events as measured by a modified Systematic Assessment for Treatment Emergent Events (SAFTEE) given at baseline and immediately post-TMS.

Hypothesis 1.c. (feasibility): At least 80% of participants will complete the study protocol.

Specific Aim 2: To examine the utility of electrophysiological and behavioral profiles as biomarkers of depression correlated with response to treatment with right-DLPFC TMS in patients with epilepsy.

Hypothesis 2a: Changes in dense array EEG based biomarkers of depression (hemispheric frontal alpha power asymmetry, anterior cingulate theta power, and frontotemporal alpha coherence) will correlate with changes in depression scores.

3 Study Design

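### At Visit 5 an EEG of about one hour is scheduled between the last TMS session and the SAFTEE that Hypothesis 1.b places immediately after treatment

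*Combined protocol and SAP*

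**What the plan says.** Section 2 words Hypothesis 1.b as no higher rate of adverse events "as measured by a modified Systematic Assessment for Treatment Emergent Events (SAFTEE) given at baseline and immediately post-TMS". Section 3.2 lists change on this scale as primary endpoint 2.

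The visit descriptions place the end-of-day SAFTEE as follows.

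- Visit 3 (section 6.4): "Following the final TMS session, study personnel will administer the SAFTEE, and PANAS".
- Visit 4 (section 6.5): the SAFTEE and PANAS come under the line "At the end of the final treatment session, research staff will".
- Visit 5 (section 6.6): "Once the final TMS treatment session is complete, a second dense-array EEG test will be conducted, which will last approximately one hour". The next line begins "After completion of the dense-array EEG, research staff will", and the first task under it is "Administer the SAFTEE, PANAS, QIDS, and MoCA".

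A note at the end of section 6.6 lets patients who have not finished the 15 sessions return for one more day. It mentions no SAFTEE for that day. Section 7.1 compares the SAFTEE before and after TMS without saying which assessment is the baseline or which is the post-treatment score.

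**The concern.** The SAFTEE is the measure to which the protocol attaches the word *immediately*, yet on the last planned day the slot directly after stimulation goes to the EEG. Two things could follow. Short-lived effects of the final sessions may have faded by the time the scale is given. Any complaint that starts during the recording would be entered on the same form and could not be told apart from an effect of TMS.

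Section 5.2 puts every patient in the treatment group, and section 5.5 confirms that nobody is blinded. In an uncontrolled before/after comparison nothing balances assessment timing or other procedures on the same day, so either distortion would carry straight into a primary safety endpoint. The two would act in opposite directions and could not be separated afterwards.

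**Working it through.** There is no plan figure to reproduce. Section 7.2 covers the proportion with an SAE and the depression comparison, and gives nothing for the SAFTEE. The check is a comparison of the schedule across visits, using the planned session counts in section 5.1.

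| Day | Planned sessions | Cumulative, of 15 | Scheduled between last session and SAFTEE |
|---|---|---|---|
| Visit 3 | 4 | 4 | nothing |
| Visit 4 | 7 | 4 + 7 = 11 | nothing |
| Visit 5 | 4 | 11 + 4 = 15 | dense-array EEG, about one hour |
| Optional fourth day | the remainder | 15 | no SAFTEE stated |

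1. **Delay.** The planned gap at Visit 5 is about 60 minutes, against no scheduled procedure at Visits 3 and 4. Whether the hour includes fitting the electrodes is not stated.

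2. **What the Visit 5 score is.** It is the first SAFTEE after the full planned course. The next is the telephone contact one to two weeks later (section 6.7). The Visit 3 and 4 scores follow 4 and 11 of 15 planned sessions, so they inform on acute effects but do not follow the complete course.

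3. **The baseline side.** The pre-treatment SAFTEE at Visit 3 has no EEG scheduled before it that day. The other candidate, at Visit 1b, may fall on the same day as the Visit 2 procedures, which include an EEG (section 6.2). With Visit 3 as baseline, the before and after scores are therefore taken under different same-day conditions.

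4. **Which measure needs the first slot.** Sections 3.1 and 5.1 ask for an EEG before and after the course, with no requirement that it be immediate. Section 3.1 calls the EEG aim secondary, although section 3.2 lists the biomarker correlation as item 4 under the primary endpoints. Only the SAFTEE carries a stated requirement of immediacy.

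5. **Size of the bias.** It cannot be computed. The documents give no duration for TMS side effects, no recall period for the SAFTEE and no rate of complaints from the EEG.

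**The case against.** The strongest reply is that the Visit 5 SAFTEE already satisfies Hypothesis 1.b. *Immediately* is given no time limit. Section 4.3.2 uses the same word as the label of a time point, ahead of one week, one month and three months. Read that way, an assessment at the same visit qualifies. This stands: a reader might infer that the Visit 5 score fails the hypothesis outright, and the text does not support that. What remains is that an hour-long scheduled procedure sits poorly with the word, and that the plan does otherwise on the two preceding days.

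A reader might also infer that the score does mix EEG effects with TMS effects. The documents report no symptoms from the EEG, which section 5.1 describes as a resting recording with eyes closed. Mixing is possible, not shown.

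Nor do the documents support putting a number on what is lost. Assumed half-lives of 0.5, 1 and 2 hours would leave 0.5^(1/0.5) = 25%, 0.5^(1/1) = 50% and 0.5^(1/2) = 71% after one hour. But the half-lives are invented, and the sum presumes that the SAFTEE records only what is felt at that moment. Section 3.3 does not say so, and telephone use at one week and three months fits poorly with it. Each end-of-day score also already looks back over 4 × 50 = 200 or 7 × 50 = 350 minutes of stimulation, plus breaks, so an extra hour is not a change from zero.

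Other safeguards also stand. The SAFTEE is given before treatment at Visits 4 and 5 and again at Visits 6 to 9, so Visit 5 is not the only score after the course. Staff deliver and watch every session (section 5.3), and adverse events are asked about at each contact (section 8.4).

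Finally, giving the EEG first could be defended because its biomarkers appear in section 3.2. That is a fair reason to keep the EEG delay short. It does not outweigh the protocol's description of safety as the main purpose. The Study Visit Guide and Study Procedures Table are listed as attachments but were not available, so whether they set a different order is unknown.

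**Conclusion.** The point holds as a minor inconsistency in scheduling and definition. The order in section 6.6 puts about one hour and a separate procedure between the end of the planned course and the SAFTEE, unlike Visits 3 and 4, and does so for a primary safety measure with no control arm. Bias in either direction is possible. Its size is unknown, and the Visit 3 and 4 scores limit what could be missed. The endpoint is not invalidated, and sample size and power are unaffected.

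The gap in section 7.1 adds to the problem: without a named baseline and post-treatment score, the analyst could choose among several. Fixing the label to Visit 5 would not be enough, because a patient who returns for a fourth day has not finished treatment at Visit 5.

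The conclusion rests on the visit descriptions being followed in the order written.

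**What to change.** - **Section 6.6:** after the final session give the SAFTEE and PANAS, then the EEG, then the QIDS and MoCA.
- **Optional fourth day:** schedule a SAFTEE after the last session, before any EEG done that day.
- **Section 7.1:** define the post-TMS score for Hypothesis 1.b as the SAFTEE given after the last session actually delivered and before the EEG. Name the Visit 3 pre-treatment SAFTEE as the baseline.

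For patients who finish in three days this adds no assessment; for those who return it adds one SAFTEE. The cost is that the EEG starts later by the time the two scales take. The documents do not give that time, and 10 to 20 minutes is assumed. Since the biomarker correlation is also a listed endpoint, the delay should be acknowledged, but it would be similar for all patients.
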